## 6.3 Accrual and sample size

This study will enroll up to 15,600 participants into four groups defined by baseline HIV-1 and SARS-CoV-2 sero-statuses and randomized to receive the same vaccination series of mRNA-1273 at month 0 and month 1 (if applicable), but two different vaccines (mRNA-1273 or mRNA-1273.222) at month 6 at a 1:1 randomization ratio within each group as shown in the study schema. The sample sizes of Groups 1 and 2 are driven by the total number of COVID-19 cases that are needed to achieve sufficient statistical power to evaluate the relative risk of COVID-19 between Groups 1 and 2 in the pre-Month 6 stage, as well as between randomized interventions at Month 6 within each group in the post-Month 6 stage. The sample sizes of Groups 3 and 4 are primarily driven by the precision to characterize safety and immunogenicity of the regimens in each group of participants while keeping the same 1:2 ratio between the SARS-CoV-2 negative and positive groups as for Groups 1 and 2.

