3. POST-MONTH 6 STAGE : to assess the relative risk of symptomatic COVID-19 and of severe COVID-19 after the Month 6 dose in Group 1 (PLWH who are SARS-CoV-2 negative at baseline) and Group 2 (PLWH who are SARS-CoV-2 positive at baseline), separately and combined, among those who received mRNA-1273 at Month 6 vs. those who received mRNA-1273.222 at Month 6, counting endpoints at least 14 days after the Month 6 dose until end of follow up.	COVID-19 and severe COVID-19 as defined for the primary endpoints
4. POST-MONTH 6 STAGE : to assess the relative risk of virologically confirmed symptomatic COVID-19 and of severe COVID-19 after the Month 6 dose in Groups 1 and 3 together (participants who are SARS-CoV-2 negative at baseline regardless of HIV status) and in Groups 2 and 4 together (participants who are SARS-CoV-2 positive at baseline regardless of HIV status), respectively, among those who received mRNA-1273 at Month 6 vs. those who received mRNA-1273.222 at Month 6, counting endpoints at least 14 days after Month 6 dose until the end of follow up.	COVID-19 and severe COVID-19 as defined for the primary endpoints
5. PRE-MONTH 6 & POST-MONTH 6 STAGES : to assess the relative risk of symptomatic COVID-19 and of severe COVID-19 after the Month 6 dose by neutralization phenotype and Spike sequence features of acquired SARS-CoV-2 viruses (sieve analysis) in Groups 1 and 3 together (participants who are SARS-CoV-2 negative at baseline regardless of HIV status) and in Groups 2 and 4 together (participants who are SARS-CoV-2 positive at baseline regardless of HIV status), respectively, among those who received mRNA-1273 at Month 6 vs. those who received mRNA-1273.222 at Month 6, counting endpoints starting 1 day after dose 1, 14 days after the last pre-Month6 dose , or 14 days after Month 6 dose until the end of follow up.	COVID-19 and severe COVID-19 as defined for the primary endpoints; neutralization phenotypes and viral genotypic characteristics of SARS-CoV-2 at diagnosis.

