### 6.3.1 Power calculations for coprimary objectives 1-4 (Efficacy)

Let  $VE(COVID)$  and  $VE(Severe\ COVID)$  denote vaccine efficacy of the vaccine regimen vs. counterfactual placebo among baseline SARS-CoV-2 negative participants against COVID-19 and severe COVID-19, respectively. The relative risk objectives are assessed in terms of cumulative incidence ratios between the active vaccine regimens without analysis of counterfactual placebo arms; the notations  $VE(COVID)$  and  $VE(Severe\ COVID)$  are mainly used for purposes of communicating effect sizes.

The following calculations focus on the COVID-19 endpoint because the severe COVID-19 endpoint could potentially be changed to be a secondary endpoint if there are insufficient severe COVID endpoints (Section 6.4.3). For the assessment of pre-Month 6 stage objectives, sample sizes of Groups 1 and 2 in the FAS are considered. For the assessment of post-Month 6 stage objectives, the following calculations consider approximately 4000 participants in Groups 1-4 received their Month 6 vaccination (mRNA-1273 vs. mRNA-1273.222) per randomization under protocol version 6. This sample size is consistent with study data as of June 2023. As shown in the upper portion (pre-Month 6 stage) of Table 6-2, there is ample power ( $> 90\%$ ) to detect a relative risk of 2.0 between Groups 1 and 2 against the null hypothesis  $H_0: RR = 1.0$  during Month 0 and 6 in the pre-Month 6 stage. In reality, the sample sizes of the PLWH hybrid immunity group who receive 1 pre-Month 6 dose and the PLWH pure vaccine group who receive 2 pre-Month 6 doses are likely smaller than the sample sizes of Groups 1 and 2, respectively. As shown in the lower portion (post-Month 6 stage) of Table 6-2, when the annual incidence of the primary endpoint is in the range of 2.5%- 3.5% in the mRNA-1273 arm, there is approximately 80-90% power to detect a relative risk of 2.0 – 2.5 between mRNA-1273 vs. mRNA-1273.222 vaccination during Month 6.5 and 18 in the post-Month 6 stage.

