These calculations are carried out assuming 5% annual dropout, 5% probability of missing any of the 3 doses, VE(COVID) of 63% between Month 0 and Month 6 in Group 1 (SARs-CoV-2 negative) and in Group 2, and 5% six-month COVID-19 incidence rate among unvaccinated PLWH SARs-CoV-2 negative individuals in the community. The assumption on VE(COVID) of 63% between Month 0 and Month 6 accounts for a possible reduced protection of the vaccine regimen in PLWH against the SARS-CoV-2 variant at the time of the trial conduct. The 5% six-month background incidence rate assumption was based on the observed 4.7%, 5.25%, and 10.38% placebo arm six-month incidence rates among baseline SARS-CoV-2 negative participants in, respectively, the AstraZeneca phase 3 (149), Novavax phase 2 (107), and Janssen ENSEMBLE phase 3 (28) trials restricted to South African study sites, and building in conservative margin given the availability of vaccines to potentially reduce transmission and infection in the region. The background SARS-CoV-2 (re-infection) incidence rate among unvaccinated PLWH SARS-CoV-2 positive individuals in the community is assumed to be half of that of unvaccinated PLWH SARS-CoV-2 negative individuals based on the reported protection of approximately 55% against the Omicron variant from previous SARS-CoV-2 infection in South Africa (150-152) and in other countries (153). The statistical power is calculated using an exact binomial test with a (two-sided) false positive error rate of 0.05.

**Table 6-2 Pre-Month 6 stage:** power to detect relative risk (Months 0-6) being different from 1.0 between Group 1 (n=4200) and Group 2 (n=8400).

True VE (0-6) of Group 1 (n=4200)	Relative Risk (Groups 1 vs. 2)	Total expected number of events M0-6	Power
60%	1.3	189	45%
	1.6	176	85%
	2.0	167	99%
70%	1.2	149	17%
	1.5	135	59%
	2.0	125	96%
70%	1/1.3	207	45%
75%	1/1.6	203	85%
80%	1/2.0	200	99%
75%	1/1.2	159	17%
80%	1/1.5	153	59%
85%	1/2.0	150	96%

**Post-Month 6 stage:** power to detect relative risk (Months 6.5-18) being different from 1.0 between mRNA-1273 vs. mRNA-1273.222 Month 6 vaccination (n=4000, 2000 vs. 2000),.

Annual incidence for mRNA-1273 Month 6 vaccination arm	Relative Risk (mRNA-1273 vs. mRNA-1273.222)	Total expected number of events M6.5-18	Power
3.5%	1.5	110	54%
	2.0	106	93%
3.0%	2.0	91	87%
	2.5	90	99%
2.5%	2.0	76	78%
	2.5	75	96%

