The relative risk (of COVID-19, severe COVID-19, SARS-CoV-2 infection, or SARS-CoV-2 asymptomatic infection) is defined as the incidence rate ratio between the 2 treatment groups in the pre-Month 6 stage or between the 2 treatment arms within a group in the post-Month 6 stage. When there are at least 7 severe COVID-19 endpoints at the primary analysis for a given relative risk assessment, both COVID-19 and severe COVID-19 are used as coprimary endpoints. Otherwise, severe COVID-19 is considered as a secondary endpoint. For the final analyses of the pre-Month 6 objectives, the incidence will be compared across groups by estimating the marginalized cumulative incidence of the endpoint overtime for each group, using a causal inference method that adjusts for potential confounders and accounts for right-censoring of failure times. Under causal assumptions, the marginalized cumulative incidence equals the causal cumulative incidence, interpreted as cumulative incidence if, hypothetically, the entire study population were assigned to the given group under consideration. Sensitivity analyses may also be conducted to account for unobserved confounding factors. For the final analyses of the post-Month 6 objectives, the RR between treatment arms within each group will also be estimated. The causal inference approach used for the pre-Month 6 stage analysis may also be applied for estimating the relative risk of each endpoint for the post-Month 6 dose objectives. More details will be described in the SAP. For analyses before the final analyses, the RR may be estimated from a Poisson regression analysis for both pre- and post-Month 6 stages. To assess potential time effects of vaccine efficacy, the Nelson-Aalen method will be used to plot the estimated cumulative incidence rates over time for the comparison groups. Additional analysis of RR by specified viral

strain categories may also be performed using competing risks failure time methods, as detailed in the SAP.

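### Protocol 6.3 still says Groups 1 and 2 are sized to compare the two Month 6 vaccines within each group, but the only post-Month 6 power calculation pools Groups 1-4 and the roughly 4,000 randomised cannot deliver that power within both groups

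*Protocol*

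**What the plan says.** Protocol Section 6.3 gives the design basis: "The sample sizes of Groups 1 and 2 are driven by the total number of COVID-19 cases that are needed to achieve sufficient statistical power" for Group 1 versus Group 2 before Month 6, and "as well as between randomized interventions at Month 6 within each group in the post-Month 6 stage". The two Month 6 vaccines are allocated "at month 6 at a 1:1 randomization ratio within each group as shown in the study schema".

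Section 6.3.1 then calculates post-Month 6 power for a different population: "the following calculations consider approximately 4000 participants in Groups 1-4 received their Month 6 vaccination" per randomisation under version 6. The lower part of Table 6-2 is labelled "n=4000, 2000 vs. 2000". On the method, the section says: "The statistical power is calculated using an exact binomial test with a (two-sided) false positive error rate of 0.05". At a relative risk (RR) of 2.0 the table prints 93%, 87% and 78% for 106, 91 and 76 expected events.

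Section 6.4.3 defines the post-Month 6 relative risk as "between the 2 treatment arms within a group in the post-Month 6 stage", yet the same section runs the primary post-Month 6 analysis across all groups. Secondary objective 3 (Section 3) asks for Groups 1 and 2 "separately and combined, among those who received mRNA-1273 at Month 6 vs. those who received mRNA-1273.222 at Month 6". Neither document gives expected events or power for the Month 6 comparison within Group 1 or within Group 2. Table 6-3 gives precision by total endpoints, and the SAP has no power calculation.

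**The concern.** The design statement, the definition of the relative risk and the power calculation do not describe the same comparison. Section 6.3 claims power within each group; Section 6.3.1 shows power only for the pool.

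This matters for secondary objective 3. Protocol Section 2.1 names as important whether people with hybrid and vaccine-only immunity respond differently to the bivalent vaccine. A reader who relies on Section 6.3 would take Groups 1 and 2 to be adequately sized on their own, and could read a non-significant result in one of them as evidence of no bivalent benefit there. With the events to be expected, such a result would carry little information.

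**Working it through.** **Inputs.** Test: two-sided exact binomial, 5%, allocation 1:1 (6.3, 6.3.1). Event totals D at RR 2.0: 106, 91 and 76 for annual incidence 3.5%, 3.0% and 2.5% in the mRNA-1273 arm (Table 6-2). Ceiling group sizes: 4,200, 8,400, 1,000 and 2,000, total 15,600 (Table 1-1). Interim annual incidences, Groups 1-4: 7.1%, 2.2%, 5.8% and 1.5% (2.1).

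**Step 1: reproduce the printed power.** Given D events, those in the mRNA-1273 arm are binomial with p = 0.5 under the null and p = RR/(1+RR) = 2/3 at RR 2.0. Rejecting at 0.025 per tail:
- D = 106, 91, 76 at RR 2.0: 92.9%, 87.4%, 78.1% (printed 93, 87, 78).
- D = 110 at RR 1.5: 54.1% (printed 54).
- D = 90 and 75 at RR 2.5: 98.7% and 96.2% (printed 99 and 96).

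The printed powers are therefore those of the pooled test.

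**Step 2: the Section 6.3 claim at ceiling sizes.** Scale D by group size over 4,000.
- Group 1, factor 4,200/4,000: 111.3, 95.5 and 79.8 events; power 93%, 88%, 82%.
- Group 2, factor 8,400/4,000: 222.6, 191.1 and 159.6 events; power about 99% or more throughout.

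The sentence is correct for those sizes.

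**Step 3: the same test on each group's share of the 4,000 (RR 2.0).** The split is not in the documents, so three are tried. The first power takes D fixed at a neighbouring whole number; the second takes D as Poisson with the stated mean.
- Schema shares, equal incidence: Group 1 4,200/15,600 = 26.9%, Group 2 8,400/15,600 = 53.8%.
- Interim incidences, size times incidence: Group 1 4,200 × 7.1 = 29,820; Group 2 8,400 × 2.2 = 18,480; Group 3 1,000 × 5.8 = 5,800; Group 4 2,000 × 1.5 = 3,000; sum 57,100. Shares: Group 1 52%, Group 2 32%.
- Section 6.3.1's assumption that seropositive background incidence is half, applied to both HIV strata: 4,200 : 4,200 : 1,000 : 1,000, so Groups 1 and 2 have 40% each.

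| Split | Group | Events (3.5 / 3.0 / 2.5%) | Power, fixed D | Power, Poisson D |
|---|---|---|---|---|
| Schema shares | 1 | 28.5 / 24.5 / 20.5 | 33 / 26 / 30% | 35 / 30 / 25% |
| Schema shares | 2 | 57.1 / 49.0 / 40.9 | 67 / 64 / 49% | 68 / 60 / 52% |
| Interim incidences | 1 | 55.4 / 47.5 / 39.7 | 64 / 57 / 53% | 66 / 59 / 50% |
| Interim incidences | 2 | 34.3 / 29.5 / 24.6 | 39 / 33 / 37% | 43 / 37 / 30% |
| Half background | 1 and 2 each | 42.8 / 36.8 / 30.7 | 53 / 53 / 38% | 54 / 46 / 38% |

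**Step 4: a bound free of the split.** At least one of Groups 1 and 2 gets no more than half the events: 53, 45 or 38. Power at exactly those counts is 60%, 57% and 48%, but these are not maxima, because exact power is not monotone in D. The largest values over all counts up to half are 68% (51 events), 61% (44) and 53% (37).

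**Step 5: what would be needed.** Exact power at RR 2.0 stays at or above 80% from 77 events in a group. Table 6-2's lowest row expects 76 in the whole comparison.

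**Step 6: precision.** For an observed RR of 2.0 take exp(ln 2 ± 1.96 × √(3/(2D) + 3/D)). With D = 50 this gives 1.11 to 3.60, as printed in Table 6-3. Under schema shares, Group 1 gives 0.92-4.36, 0.86-4.63 and 0.80-5.01; Group 2 gives 1.15-3.47, 1.10-3.62 and 1.04-3.83.

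**The case against.** The strongest reply is that nothing was miscalculated. Section 6.3 explains the ceiling sizes, and Step 2 confirms it for them. Section 6.3.1 states both the reduced number and the pooling, and Table 6-2's caption repeats it, so the table does not present 78-93% as within-group power. The primary post-Month 6 comparison is pooled, and the SAP (7.1 and 11.4.1) stratifies its Cox model by the four study groups. Section 6.4.3 speaks of estimating the relative risk within each group, and Table 6-3 gives precision by endpoint count. SAP Table 2 lists no bivalent-versus-monovalent analysis in Group 1 or Group 2 alone; its subgroups are people with and without HIV. Where fewer than 20 COVID-19 endpoints occur, the SAP falls back to description.

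All of that stands, and it rules out stronger readings. A reader might infer that Table 6-2 is wrong or that primary objective 3 is underpowered; the table's powers reproduce for the pooled comparison. A reader might infer that the SAP plans underpowered tests in Groups 1 and 2; its listed analyses include none. A reader might take one within-group percentage as fact; each rests on an assumed split. Nor would group-level power answer whether hybrid and vaccine-only people respond differently, which is a question of interaction.

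The reply does not rescue the sentence in Section 6.3. It stands in the current version, in the present tense, beside a calculation for about 4,000 people that does not support it, and secondary objective 3 still asks for the two groups separately.

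**Conclusion.** The point holds as an outdated power claim, not an arithmetic error. The within-group statement was true at 4,200 and 8,400 and is not true for the roughly 4,000 randomised under version 6. At RR 2.0, against a pooled 78-93%, within-group power is about 25-35% (Group 1) and 49-68% (Group 2) under schema shares, or about 50-66% and 30-43% under the interim incidences. These ranges assume the split, Table 6-2's event totals and a true RR of 2.0 in the group. The conclusion does not depend on the split: at least one of the two groups cannot exceed about 68%, 61% or 53%.

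The consequence is confined to secondary objective 3 and to the consistency of Sections 6.3, 6.3.1 and 6.4.3.

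**What to change.** - In 6.3, remove the claim of sufficient power within each group, and state that Table 6-2's post-Month 6 power applies only to the comparison pooled over Groups 1-4.
- Beside Table 6-2, give expected events and power, or confidence-interval width, for Groups 1 and 2, using the numbers actually randomised in each under version 6.
- Describe the group-specific relative risks of secondary objective 3 as estimates with 95% confidence intervals, not powered tests.
- In 6.4.3, align the definition of the post-Month 6 relative risk with the primary comparison stated there, pooled across groups, and with the group-stratified model in SAP 7.1 and 11.4.1. Keep the within-group relative risk as a secondary quantity.

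The cost is wording and a short recalculation, with no new participants or data. The downside is that the stated within-group power becomes less favourable.

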### 6.3.1 Power calculations for coprimary objectives 1-4 (Efficacy)

Let  $VE(COVID)$  and  $VE(Severe\ COVID)$  denote vaccine efficacy of the vaccine regimen vs. counterfactual placebo among baseline SARS-CoV-2 negative participants against COVID-19 and severe COVID-19, respectively. The relative risk objectives are assessed in terms of cumulative incidence ratios between the active vaccine regimens without analysis of counterfactual placebo arms; the notations  $VE(COVID)$  and  $VE(Severe\ COVID)$  are mainly used for purposes of communicating effect sizes.

The following calculations focus on the COVID-19 endpoint because the severe COVID-19 endpoint could potentially be changed to be a secondary endpoint if there are insufficient severe COVID endpoints (Section 6.4.3). For the assessment of pre-Month 6 stage objectives, sample sizes of Groups 1 and 2 in the FAS are considered. For the assessment of post-Month 6 stage objectives, the following calculations consider approximately 4000 participants in Groups 1-4 received their Month 6 vaccination (mRNA-1273 vs. mRNA-1273.222) per randomization under protocol version 6. This sample size is consistent with study data as of June 2023. As shown in the upper portion (pre-Month 6 stage) of Table 6-2, there is ample power ( $> 90\%$ ) to detect a relative risk of 2.0 between Groups 1 and 2 against the null hypothesis  $H_0: RR = 1.0$  during Month 0 and 6 in the pre-Month 6 stage. In reality, the sample sizes of the PLWH hybrid immunity group who receive 1 pre-Month 6 dose and the PLWH pure vaccine group who receive 2 pre-Month 6 doses are likely smaller than the sample sizes of Groups 1 and 2, respectively. As shown in the lower portion (post-Month 6 stage) of Table 6-2, when the annual incidence of the primary endpoint is in the range of 2.5%- 3.5% in the mRNA-1273 arm, there is approximately 80-90% power to detect a relative risk of 2.0 – 2.5 between mRNA-1273 vs. mRNA-1273.222 vaccination during Month 6.5 and 18 in the post-Month 6 stage.

These calculations are carried out assuming 5% annual dropout, 5% probability of missing any of the 3 doses, VE(COVID) of 63% between Month 0 and Month 6 in Group 1 (SARs-CoV-2 negative) and in Group 2, and 5% six-month COVID-19 incidence rate among unvaccinated PLWH SARs-CoV-2 negative individuals in the community. The assumption on VE(COVID) of 63% between Month 0 and Month 6 accounts for a possible reduced protection of the vaccine regimen in PLWH against the SARS-CoV-2 variant at the time of the trial conduct. The 5% six-month background incidence rate assumption was based on the observed 4.7%, 5.25%, and 10.38% placebo arm six-month incidence rates among baseline SARS-CoV-2 negative participants in, respectively, the AstraZeneca phase 3 (149), Novavax phase 2 (107), and Janssen ENSEMBLE phase 3 (28) trials restricted to South African study sites, and building in conservative margin given the availability of vaccines to potentially reduce transmission and infection in the region. The background SARS-CoV-2 (re-infection) incidence rate among unvaccinated PLWH SARS-CoV-2 positive individuals in the community is assumed to be half of that of unvaccinated PLWH SARS-CoV-2 negative individuals based on the reported protection of approximately 55% against the Omicron variant from previous SARS-CoV-2 infection in South Africa (150-152) and in other countries (153). The statistical power is calculated using an exact binomial test with a (two-sided) false positive error rate of 0.05.

**Table 6-2 Pre-Month 6 stage:** power to detect relative risk (Months 0-6) being different from 1.0 between Group 1 (n=4200) and Group 2 (n=8400).

True VE (0-6) of Group 1 (n=4200)	Relative Risk (Groups 1 vs. 2)	Total expected number of events M0-6	Power
60%	1.3	189	45%
	1.6	176	85%
	2.0	167	99%
70%	1.2	149	17%
	1.5	135	59%
	2.0	125	96%
70%	1/1.3	207	45%
75%	1/1.6	203	85%
80%	1/2.0	200	99%
75%	1/1.2	159	17%
80%	1/1.5	153	59%
85%	1/2.0	150	96%

**Post-Month 6 stage:** power to detect relative risk (Months 6.5-18) being different from 1.0 between mRNA-1273 vs. mRNA-1273.222 Month 6 vaccination (n=4000, 2000 vs. 2000),.

Annual incidence for mRNA-1273 Month 6 vaccination arm	Relative Risk (mRNA-1273 vs. mRNA-1273.222)	Total expected number of events M6.5-18	Power
3.5%	1.5	110	54%
	2.0	106	93%
3.0%	2.0	91	87%
	2.5	90	99%
2.5%	2.0	76	78%
	2.5	75	96%

In addition, [Table 6-3](#) provides the precision of the relative risk estimates with different numbers of endpoints accrued in the post-Month 6 stage.

**Table 6-3 Post-Month 6 Stage:** precision in relative risk (RR) estimates with 50, 100 or 150 total endpoints accrued between Month 6.5 and Month 18.

Estimate RR of COVID-19 (mRNA-1273 vs. mRNA-1273.222)	95% CI of RR		
	50 endpoints	100 endpoints	150 endpoints
1.0	(0.57, 1.74)	(0.68, 1.48)	(0.73, 1.38)
1.25	(0.72, 2.18)	(0.84, 1.85)	(0.91, 1.72)
1.5	(0.85, 2.64)	(1.00, 2.24)	(1.08, 2.08)
2.0	(1.11, 3.60)	(1.32, 3.03)	(1.42, 2.81)
2.5	(1.36, 4.62)	(1.62, 3.86)	(1.75, 3.56)
3.0	(1.58, 5.69)	(1.91, 4.72)	(2.07, 4.34)

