The interim analyses suggest that PLWH with prior SARS-CoV-2 infection who receive one dose of mRNA vaccine, are at significantly lower risk of symptomatic COVID-19 compared with those without prior infection who received a two-dose regimen. Moreover, the mRNA-1273 vaccine has been demonstrated to be safe and well tolerated by PLWH. Given this, and the fact that monovalent mRNA vaccines like mRNA-1273 will likely not be commercially available much longer (to be replaced by bivalent and other next-generation vaccines), the study authors and the Sponsor decided to end routine research follow up for most participants vaccinated with only mRNA-1273. This change in the follow-up schedule was communicated to clinical research sites in January 2023.

For the final phase of the Ubuntu study, the study will focus on participants vaccinated under protocol version 6.0 (ie, mRNA-1273 versus mRNA-1273.222, per randomization), and those with certain conditions that may increase the risk of prolonged SARS-CoV-2 infections (ie, active TB, HIV with low CD4 count, and/or HIV with unsuppressed viral load). To improve surveillance of asymptomatic infections, participants be administered nasal swab NAATs monthly, in addition to those initiated in response to symptoms or otherwise scheduled. And given the potential association between HIV disease and persistent SARS-CoV-2 infections, additional blood samples will be collected periodically among participants who are nasal swab NAAT positive for prolonged periods. Twelve months of follow up after enrolment will be adequate to accomplish the study objectives.

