Target population	Participants randomized to monovalent or bivalent under Protocol Version 6 (RM6)
Endpoint	COVE-/CDC-based COVID-19 endpoints counted 14 days after M6 vaccination
Time frame	13 days post M6 vaccination to M12/M18 visit
	Primary analysis II (applicable when # COVID-19 endpoints is at least 20)
Target population	Full per-protocol participants randomized to monovalent or bivalent under Protocol Version 6 (FPP)
Endpoint	COVE-/CDC-based COVID-19 endpoints counted 14 days after M6 vaccination
Time frame	13 days post M6 vaccination to M12/M18 visit
	Primary analysis III (applicable when # severe endpoints is at least 7)
Target population	Participants randomized to monovalent or bivalent under Protocol Version 6 (RM6)
Endpoint	Severe COVID-19 endpoints counted 14 days after M6 vaccination
Time frame	13 days post M6 vaccination to M12/M18 visit
	Primary analysis IV (applicable when # severe endpoints is at least 7)
Target population	Full per-protocol participants randomized to monovalent or bivalent under Protocol Version 6 (FPP)
Endpoint	Severe COVID-19 endpoints counted 14 days after M6 vaccination
Time frame	13 days post M6 vaccination to M12/M18 visit
	Secondary analysis I (applicable when # COVID-19 endpoints is at least 20)
Target population	Participants randomized to monovalent or bivalent under Protocol Version 6 (RM6)
Endpoint	COVE-/CDC-based COVID-19 endpoints counted 1 day after M6 vaccination
Time frame	M6 vaccination to M12/M18 visit
	Secondary analysis II (applicable when # severe endpoints is at least 7)
Target population	Participants randomized to monovalent or bivalent under Protocol Version 6 (RM6)
Endpoint	Severe COVID-19 endpoints counted 1 day after M6 vaccination
Time frame	M6 vaccination to M12/M18 visit
	Secondary analysis III
Target population	PLWH/PLWoH randomized to monovalent or bivalent under Protocol Version 6 (RM6)
Endpoint	COVE-/CDC-based/Severe (when applicable) COVID-19 endpoints counted 14 days after M6 vaccination
Time frame	13 days post M6 vaccination to M12/M18 visit
	Secondary analysis IV
Target population	PLWH/PLWoH randomized to monovalent or bivalent under Protocol Version 6 (RM6)
Endpoint	COVE-/CDC-based/Severe (when applicable) COVID-19 endpoints counted 1 day after M6 vaccination
Time frame	M6 vaccination to M12/M18 visit
	Secondary analysis V
Target population	Full per-protocol PLWH/PLWoH randomized to monovalent or bivalent under Protocol Version 6 (FPP)

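### The post-Month 6 event totals in Protocol Table 6-2 do not follow from the stated inputs, and no power is given for the Month 12 look

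*Protocol*

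**What the plan says.** Protocol Section 6.3.1 gives the inputs for the post-Month 6 stage: "the following calculations consider approximately 4000 participants in Groups 1-4 received their Month 6 vaccination", split as "mRNA-1273 vs. mRNA-1273.222 Month 6 vaccination (n=4000, 2000 vs. 2000". Annual incidence in the monovalent arm is 2.5%, 3.0% or 3.5%. On losses it says "These calculations are carried out assuming 5% annual dropout". On the test it says "The statistical power is calculated using an exact binomial test with a (two-sided) false positive error rate of 0.05".

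The column headed "Total expected number of events M6.5-18" in Table 6-2 reads 110 and 106 (3.5%; RR 1.5 and 2.0), 91 and 90 (3.0%; RR 2.0 and 2.5), and 76 and 75 (2.5%; RR 2.0 and 2.5). The stated powers, in the same order, are 54, 93, 87, 99, 78 and 96%. The text sums this up as "there is approximately 80-90% power to detect a relative risk of 2.0", and the sentence continues to RR 2.5 and is limited to Months 6.5 to 18.

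Protocol Section 2.1 says: "Twelve months of follow up after enrolment will be adequate to accomplish the study objectives". The Overview and Section 2.1.1 plan follow-up to 18 months, and Section 6.6 places the final post-Month 6 analysis at the end of follow-up. SAP Table 2 gives all four primary analyses the time frame "13 days post M6 vaccination to M12/M18 visit". SAP Section 7 calls the Month 18 analyses final and makes no adjustment for the two looks.

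**The concern.** With the number per arm and the monovalent incidence fixed, a larger relative risk means fewer bivalent cases, so the total must fall noticeably as RR rises. In Table 6-2 it hardly falls. The totals drive the power, so they should be reproducible from the inputs printed beside them.

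The second issue is what the power covers. It is given to Month 18 only, yet Section 2.1 calls twelve months from enrolment enough and the SAP reports its primary comparison at Month 12 too. A null Month 12 result would have only a Month 18 power figure to be set against.

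**Working it through.** **1. Power from the printed totals.** I used a two-sided exact binomial test conditional on the total, null p = 0.5, alternative p = RR/(1+RR). The printed totals give 54.1, 92.9, 87.4, 98.7, 78.1 and 96.2%. All six stated powers reproduce, so the test is right and the question is the totals.

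**2. Windows available.**
- Months 6.5 to 18 taken literally: 11.5/12 × 365 ≈ 350 days.
- Visit schedule: Month 6 dose on Day 169, Month 18 visit on Day 547, time origin 13 days after the dose: 547 − 169 − 13 = 365 days. SAP Section 10.2 also uses 365.
- Upper edge of the Month 18 visit window (+14, Protocol Appendix K), where SAP Section 4 censors: 379 days.

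**3. Totals from the inputs.** Without dropout, events = 2,000 × rate × T × (1 + 1/RR). With dropout, each arm with hazard h gives 2,000 × h/(h+d) × (1 − exp(−(h+d)T)), where d = −ln(0.95) = 0.0513. Example at 3.0%, RR 2.5, T = 1 year: 57.6 (h = 0.030) + 23.3 (h = 0.012) = 80.9. The 5% missed-dose allowance is not applied, because the 4,000 had already received the Month 6 dose.

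| Incidence, RR | Stated | No dropout: 350 / 365 / 379 days | 5% dropout, 350-365 days | Months implied by stated total, no dropout |
|---|---|---|---|---|
| 3.5%, 1.5 | 110 | 111.8 / 116.7 / 121.1 | 107.5-112.0 | 11.3 |
| 3.5%, 2.0 | 106 | 100.6 / 105.0 / 109.0 | 96.8-100.9 | 12.1 |
| 3.0%, 2.0 | 91 | 86.2 / 90.0 / 93.5 | 83.2-86.7 | 12.1 |
| 3.0%, 2.5 | 90 | 80.5 / 84.0 / 87.2 | 77.6-80.9 | 12.9 |
| 2.5%, 2.0 | 76 | 71.9 / 75.0 / 77.9 | 69.4-72.4 | 12.2 |
| 2.5%, 2.5 | 75 | 67.1 / 70.0 / 72.7 | 64.8-67.5 | 12.9 |

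The RR 2.5 rows exceed even 379 days with no dropout. The RR 2.0 rows are 5-10% above the dropout column. Multiplying events by dropout alone, without removing cases from the risk set, gives 102.4, 87.7 and 73.1 at 365 days, which makes them about 4% high.

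**4. A check that hardly depends on the window.** From RR 1.5 to 2.0 the total should fall to 1.5/1.667 = 0.90 of its value, a 10% drop; the table drops 3.6% (110 to 106). From RR 2.0 to 2.5 it should fall to 1.4/1.5 = 0.933, a 6.7% drop; the table drops 1.1% (91 to 90) and 1.3% (76 to 75). No single window fits all six rows.

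**5. Power at the recomputed totals.**
- RR 2.0: about 90-92% (97-101 events), 84-87% (83-87) and 74-81% (69-72).
- RR 2.5: about 96-98% (78-81) and 93-95% (65-68).

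Exact binomial power is saw-toothed, so one event more or less can move a value by several points.

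**6. Month 12.** The time at risk is 165 days (SAP Section 10.2) to 183 days (Day 365 − 169 − 13). Averaging exact power over a Poisson total:
- RR 2.0: about 47-52, 40-45 and 33-37 events at 3.5, 3.0 and 2.5% incidence; power runs from about 40% at the lowest incidence to 63% at the highest.
- RR 2.5 (3.0% and 2.5% incidence): about 60-76%.

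**The case against.** The strongest reply is that 11.5 calendar months is not the real window. The schedule gives 365 days, at which the RR 2.0 rows are one event too high before dropout (105, 90, 75 against 106, 91, 76). At 379 days with 5% dropout, the simpler calculation gives 106.2, 91.0 and 75.8, which matches them. This stands: a reader might infer that the whole panel is impossible, and the documents do not support that. The RR 1.5 row is attainable and the RR 2.0 rows can be matched on the longest window. But the same 379-day calculation gives about 118 for the RR 1.5 row and 85 and 71 for the RR 2.5 rows, against 110, 90 and 75, so the panel still fails as a set.

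The second reply is that little changes. That also stands for Month 18. A reader might infer that the final analysis is underpowered. It is not on these assumptions: the drop is a few points, and the table already prints 78% for its weakest RR 2.0 row.

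Third, the power sentence is limited to Months 6.5 to 18 and Month 18 is the final analysis, so it makes no false claim about Month 12. That is correct. Table 6-3 also gives precision for 50 endpoints (RR 2.0: 1.11 to 3.60), close to the Month 12 count at the highest incidence, although it is labelled for Months 6.5 to 18. Counting to the upper edge of the Month 12 visit window lifts RR 2.0 power to at most about 67%. It does not follow that Month 12 must become descriptive. The SAP keeps both looks deliberately, uses that word for no estimation or testing, and sets the threshold at fewer than 20 COVID-19 endpoints, below the totals expected here.

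**Conclusion.** The concern holds in a limited form. The post-Month 6 totals in Table 6-2 cannot all come from the stated inputs: the RR 2.5 rows are about 11-16% high and exceed any window in the documents, the RR 2.0 rows are about 4-10% high over 350-365 days with dropout, and the RR 1.5 row is attainable. Month 18 power is only slightly affected, so the text should read about 75-90% for RR 2.0.

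The twelve-month adequacy sentence conflicts with the 18-month design. The Month 12 look has about 40-63% power for RR 2.0 and 60-76% for RR 2.5, and neither document says so.

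These figures assume constant incidence, exponential dropout at 5% a year, exactly 2,000 per arm and no missed-dose loss; applying the 5% missed-dose factor would lower the totals a further 5%.

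**What to change.** - In Protocol Section 6.3.1, state the counting window in days and how dropout enters, and recompute the six post-Month 6 rows. With dropout over 350-365 days, RR 2.0 becomes about 97-101, 83-87 and 69-72 events with power of about 90-92, 84-87 and 74-81%. RR 2.5 becomes about 78-81 and 65-68 events with 96-98 and 93-95%. Recompute the RR 1.5 row on the same window.
- Change the summary sentence to about 75-90% for RR 2.0, with RR 2.5 reported separately.
- Reconcile the twelve-month sentence in Section 2.1 with follow-up to Month 18, or say which objectives it covers.
- Beside SAP Table 2, note that the stated power applies to Month 18, and give the Month 12 power. Both looks can stay.

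The cost is one table and a few sentences, with slightly less favourable figures. Design, conduct and data collection do not change.
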